#### **6.4.1 *Multiple Comparisons/Multiplicity***

Due to the early termination of the study no adjustments for multiple comparisons are defined. All summaries will be presented descriptively.

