11.2.2 Secondary Efficacy Analyses

The first secondary efficacy analysis will be analyzed using the F-S test (Finkelstein and Schoenfeld 1999). This method compares each subject to every other subject in a pairwise manner following the ranking of the first secondary endpoint (Ordinal Outcome Scale):

- 1) not hospitalized and no limitations of activities;
- 2) not hospitalized, with limitation of activities, home oxygen requirement, or both;
- 3) hospitalized, not requiring supplemental oxygen and no longer requiring ongoing medical care
- 4) hospitalized, not requiring supplemental oxygen but requiring ongoing medical care
- 5) hospitalized, requiring any supplemental oxygen;
- 6) hospitalized, requiring noninvasive ventilation or use of high-flow oxygen devices;
- 7) hospitalized, receiving invasive mechanical ventilation or extracorporeal membrane oxygenation (ECMO);
- 8) MI or stroke diagnosed since randomization
- 9) Death

The F-S test is based on the sum of 'scores' of subjects in the CardiolRx™ group. Where the score is 1, -1 or 0 according to whether the subject is the winner, the loser or tied, respectively, according to the hierarchy above.

In addition, the CardiolRx™ to placebo Win ratio (WR) will be calculated, as described by Pocock.(Pocock et al. 2012) For this statistic, every subject in the CardiolRx™ group is compared to every subject in the placebo group in a pairwise manner following the ranking of the first secondary efficacy endpoint. The WR is the number of pairs with CardiolRx™ subject 'wins' divided by the number of pairs with placebo subject 'wins'. The associated 95% CI will be based on the F-S test statistic to ensure consistency between the CI and the F-S test. A 95%CI for the WR entirely above 1 indicates a better outcome in the CardiolRx™ group.

Changes in hs-troponin and TNF-alpha from baseline to peak elevation during the 28-day treatment period between the two treatment groups will be analyzed using an ANCOVA with the baseline value as covariate.

Treatment effect estimates and 95% confidence intervals will be determined.

To control the family-wise Type I error rate, the Benjamini-Hochberg procedure will be applied to all secondary efficacy analyses.

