## 2 INTRODUCTION

This document describes the Statistical Analysis Plan (SAP) for the CARDIOL 100-03 Protocol (Study to evaluate the Efficacy and Safety of CardiolRx™ in Patients with COVID-19 and Cardiovascular Disease or Risk Factors [LANCER]. This is a multi-center, double-blind, randomized, placebo-controlled, parallel group design, 1:1 randomization study. In total 422 patients will be randomized (1:1) to either CardiolRx™ or placebo.

The design and methods of the CARDIOL 100-03 study are described in detail in the study protocol Amendment 3, dated September 23, 2021. The criteria for evaluation of study results and the analysis populations are defined in section 10 of the study protocol and an outline of the statistical analysis plan may be found in section 11 of the same document. The purpose of this document is to describe the analyses that will be performed in accordance with the protocol in more detail.

As the study was terminated early an abbreviated set of reporting will be generated as described herein. This plan will be approved prior to the breaking of the study blind. Changes from the protocol are noted.

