## 6 STATISTICAL METHODS

### 6.1 Sample Size Justification

Assuming that 19% of patients qualifying for the study in the placebo group would develop one or more primary outcomes, a treatment effect of lowering the event rate by 50% (i.e. only 9.5% of patients treated with CardiolRx™ would experience a primary outcome event, a two-sided alpha of 0.05 and 80% power, 211 patients per group (422 in total) would be required.

The protocol contained information to consider an adjustment to the sample size. Due to the early termination of the study no sample size re-estimation will be performed.

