### 6.2 General Statistical Methods and Data Handling

Tabulations will be produced for appropriate demographic, baseline, efficacy, and safety parameters.

Due to the early termination of the study no statistical testing will be performed, with the exception of the bio- and inflammatory marker data (see Section 9). All summaries will be presented descriptively.

Listings will be sorted by treatment and subject ID unless specified otherwise.

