### 9.2 Secondary Efficacy Analyses

Due to the early termination of the study the Win Ratio of the Ordinal Outcome scale will not be generated. Ordinal outcome scale scores will be listed and summarized for each visit.

The change from baseline in each biomarker (hs-troponin, NT-proBNP, D-dimer) and inflammatory marker (hs-CRP, ferritin, IL-1 beta, IL-6, IL-10) over time will be summarized at each time point and graphically displayed. After review of the profiles over time, the following parameters may be calculated.

Emax 7	Maximum post-baseline change* (baseline-corrected change) up to the time of the Day 7 assessment; reported to 2 decimal places.
Emax 28	Maximum post-baseline change* (baseline-corrected change) up to the time of the Day 28 assessment; reported to 2 decimal places.
AUEC0-7	Area under the change from baseline curve from time zero to the Day 7

AUEC0-28	assessment; calculated using the linear trapezoidal rule; reported to 3 significant figures.
	Area under the change from baseline curve from time zero to the Day 28 assessment; calculated using the linear trapezoidal rule; reported to 3 significant figures.

\*maximum post-baseline change will be positive for biomarkers that increase relative to baseline over the time interval; or negative for those that decrease relative to baseline.

Assumptions for AUEC calculation:

- Time points other than pre-dose will use actual time point instead of nominal time points. If actual assessment time is missing the nominal time will be used.
- Values missing at time points after baseline and prior to last time point in the interval will not be imputed.
- If data at last time point is missing, AUEC will be calculated up to latest non-missing time point.
- AUEC calculation will not include unscheduled and repeat measurements.

Comparison of each parameter between the two treatment groups using an ANCOVA with fixed factors for treatment and the baseline value as covariate will be performed.

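### The SAP's only retained tests are up to 32 marker ANCOVAs, with no multiplicity adjustment, no exploratory label and no fixed parameter list

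*SAP*

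**What the plan says.** SAP 6.2, repeated in 6.4, states that "no statistical testing will be performed, with the exception of the bio- and inflammatory marker data". SAP 9.2 then names three biomarkers (hs-troponin, NT-proBNP, D-dimer) and five inflammatory markers (hs-CRP, ferritin, IL-1 beta, IL-6, IL-10). It offers four derived parameters: Emax 7, Emax 28, AUEC0-7 and AUEC0-28. These are optional, and the choice follows inspection of the profiles. The section closes with "Comparison of each parameter between the two treatment groups using an ANCOVA", adjusted for baseline.

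On multiplicity, SAP 6.4.1 says that "no adjustments for multiple comparisons are defined", giving early termination as the reason and describing all summaries as descriptive. SAP 10, the section for changes to planned analyses, says that no inferential testing will be done.

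The protocol has two rules. Section 11.2.2 says: "To control the family-wise Type I error rate, the Benjamini-Hochberg procedure will be applied to all secondary efficacy analyses". Section 4.1.4 lists three such endpoints: the win ratio on the ordinal scale, peak change in hs-troponin and peak change in TNF-alpha. For the other efficacy endpoints, section 10.1.3 plans nominal, unadjusted p-values and calls the results supportive rather than confirmatory.

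**The concern.** The reason given for dropping adjustment does not fit the tests that remain. A between-arm ANCOVA with a p-value is inference, so SAP 6.4.1 and SAP 10 both conflict with 6.2, 6.4 and 9.2. A reader of section 10 alone would not learn that any test was kept, or that the one retained secondary endpoint had lost its planned adjustment.

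These p-values are also the only ones the trial will produce. Under the protocol the exploratory markers sat below a tested primary endpoint and adjusted secondary endpoints, with an explicit supportive label. The SAP removes that structure, does not repeat the label, and places all the marker tests under its secondary efficacy heading. It also leaves the set of parameters open until the profiles have been seen, and does not say whether that review is blinded to treatment. A single small p-value from such a set could be given more weight than it can bear.

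**Working it through.** **The plan's own figure.** The documents give no error rate for the marker tests. The only quantitative design statement is the sample size: "a two-sided alpha of 0.05 and 80% power, 211 patients per group (422 in total) would be required", for 19% against 9.5%. With the pooled-variance formula:

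n = [1.960·√(2 × 0.1425 × 0.8575) + 0.842·√(0.19 × 0.81 + 0.095 × 0.905)]² / 0.095² = (0.969 + 0.412)² / 0.009025 ≈ 211.4

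That rounds up to 212 against 211 stated, and power at 211 per group is 79.9%, so the figure is reproduced. It concerns the primary endpoint and says nothing about the markers.

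**Number of tests.** 8 markers × 4 parameters = 32 at most (SAP 9.2). Against the protocol they divide as follows:

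| SAP parameter | Tests | Status in the protocol |
|---|---|---|
| Emax 28, hs-troponin | 1 | Secondary endpoint, Benjamini-Hochberg (4.1.4, 11.2.2) |
| Emax 28, other seven markers | 7 | Other endpoint, nominal p (4.1.5, 10.1.3) |
| AUEC0-7, all eight | 8 | Other endpoint, nominal p (4.1.5, 10.1.3) |
| Emax 7 and AUEC0-28, all eight | 16 | No counterpart; new in the SAP |

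Of the other two endpoints in the protocol's adjusted family, the win ratio will not be generated and TNF-alpha is absent from the SAP 9.2 marker list.

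**Per-test level.** Two-sided 0.05 is assumed. The SAP states none, and the 0.05 rule in Protocol 11.4 covers the primary outcome only.

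**Independent tests.** The chance of at least one p < 0.05 when no marker is affected is 1 − 0.95^k:

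- k = 32: 1 − 0.1937 = 80.6%, with 32 × 0.05 = 1.6 false positives expected
- k = 16 (two parameters per marker): 56.0%
- k = 8 (one parameter per marker): 33.7%

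**Correlated tests.** The documents give no correlations, so these are assumed. Simulating 32 null normal test statistics (200,000 replicates per setting) gave:

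| Within-marker r | Between-marker r = 0 | 0.3 | 0.5 | 0.7 |
|---|---|---|---|---|
| 0.5 | 74.1% | 69.3% | 61.2% | 50.0% |
| 0.7 | 67.3% | 62.0% | 54.0% | 42.9% |
| 0.8 | 62.2% | 56.7% | 48.7% | 38.3% |
| 0.9 | 54.3% | 49.1% | 41.7% | 32.2% |

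A patient-level null simulation used 8 markers at baseline and Days 3, 5, 7 and 28, with an assumed 30 patients per arm. It derived the four parameters, fitted the ANCOVAs, and gave 42% to 65%.

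**Effect of adjusting.**

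- Bonferroni over 32 requires p < 0.05/32 = 0.0016, which gives 4.9% if the tests are independent. Holm has the same first step, so its chance of any rejection when no marker is affected is the same.
- Benjamini-Hochberg over all 32 gave about 2% to 5% across the simulated settings.
- Reinstating only the protocol's rule would put one test at 0.05/3 at the strictest and leave 31 at 0.05: 1 − (1 − 0.0167) × 0.95^31 = 80.0%, against 80.6% without it.

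**The case against.** The strongest reply is that Protocol 10.1.3 already planned nominal p-values for most of these markers, so the SAP is largely following the protocol. That stands for 15 of the 32 tests. It rules out a stronger reading that a reader might infer: that the SAP stripped the protocol's protection from the whole marker family and so caused the inflation. Only one of the 32 tests was ever protected, and the 80.0% against 80.6% comparison shows that losing that protection explains almost none of the risk. The risk comes from the number of unadjusted tests and the open choice of parameters.

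It is also fair to say that the SAP sets no significance level and proposes no claim, that 32 is a ceiling, and that exploratory p-values can be read as exploratory. The documents therefore do not support saying that a significant marker would be uninterpretable, or that one will be promoted. Nor was the lack of adjustment hidden: SAP 6.4.1 states it openly.

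The reply leaves four things unanswered. The justification in 6.4.1 is wrong for the tests retained. Section 10 contradicts the rest of the SAP. The supportive label that made nominal p-values acceptable in the protocol is not carried over. And 16 of the possible tests are not protocol endpoints, so 10.1.3 does not cover them.

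**Conclusion.** The point holds as a fault of internal consistency and labelling, with a real but conditional error-rate consequence. The consistency faults rest on the text alone. The percentages in the working apply only if p < 0.05 is treated as a finding, and the correlated results also depend on correlations that I assumed. If all 32 tests are run, a chance result somewhere is about as likely as not under moderate to strong correlation. It is more likely than that if the tests are close to independent, and roughly one in three if a single parameter per marker is used. Adding TNF-alpha would raise the ceiling to 9 × 4 = 36 tests and the independent figure to 84.2%. This should be corrected, but it does not undermine the rest of the abbreviated reporting.

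**What to change.** Before unblinding:

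1. In SAP 9.2, list the markers and parameters that will be tested, and remove the option to choose them after seeing profiles. Settle at the same time whether TNF-alpha belongs on the list.
2. In SAP 6.4.1, replace the current paragraph with a rule along these lines: all ANCOVAs on the fixed list form one family; nominal p-values are shown and labelled exploratory; beside each stands an adjusted value across the family (Holm p-values, or false-discovery q-values labelled as such); no marker effect is claimed on a nominal p-value alone. The labelling matters because Benjamini-Hochberg controls the false discovery rate, although the protocol describes it as family-wise control.
3. In SAP 10, state that the marker ANCOVAs are retained, that Emax 7 and AUEC0-28 are additions, and that the handling of hs-troponin peak change differs from Protocol 11.2.2.

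The cost is one rewritten paragraph, two small edits and one extra column per marker table. The downside is that fewer nominally significant markers can be highlighted. A shorter list softens this: with one parameter per marker, the first Holm threshold is 0.05/8 = 0.00625 instead of 0.0016.

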#### **6.4.2 *Subpopulations***

Section 11.5 of the protocol defined planned subgroups for exploration of the primary endpoint. Due to the early termination of the study no subgroups will be explored.

### **6.5 *Handling of Unscheduled Visits***

Visit data will be presented using nominal times as collected in the eCRF. Both scheduled and unscheduled post-baseline visits will be tabulated. Unscheduled visits will be presented as 'Visit.x.xx' (e.g. Visit 3.01).

### **6.6 *Handling of Missing Information***

#### **6.6.1 *Incomplete Calendar Dates***

All rules explained below for partial / missing dates will be followed unless contradicted by any other data recorded on the electronic Case Report Form (eCRF).

All dates presented in the individual subject listings will be as recorded on the eCRF (i.e., not completed as per the below rules).

#### **Missing / Partial Start / Stop Date of Medical History, Adverse Events (AE)**

Missing and partial start and stop date will be imputed for analysis purposes as follows.

Partial or missing stop date will be imputed as follows:

If the stop date is completely missing and the event has resolved, or the subject has stopped taking the concomitant medication, the stop date will be imputed as the date of the subject's last clinic visit in the study regardless of whether remote or in-office visit.

- If only the year is known, the stop date will be imputed as "31-Dec" of that year or as the date of the subject's last clinic visit in the study if in the same year.
- If the month and year are known, the stop date will be imputed as the last day of that month unless the stop date corresponds to the same month as the subject's last clinic visit in which case the date of subject's last clinic visit in the study will be used instead.

Missing start date will be imputed as follows:

- If the stop date occurs on or after the start of study drug or the event / concomitant medication is ongoing, the start date will be imputed as the date of the first dose of study drug.
- If the stop date occurs before the start of study drug, the start date of the event / concomitant medication will be imputed as the subject's screening date or the stop date of the event / concomitant medication whichever the earlier.

Partial start date (year present, but month and day missing)

- If the stop date occurs on or after the start of study drug or the event / concomitant medication is ongoing, and the year is the same as the year of first dosing the start date will be imputed as "01-Jan" of the same year or the date of the first dose of study drug whichever is latest. If the year is different from the year of first dosing "01-Jan" will be used.
- If the stop date occurs before the start of study drug, the start date of the event / concomitant medication will be imputed as the "01-Jan" of the same year.

Partial start date (month and year present, but day missing)

- If the stop date occurs on or after the start of study drug or the event / concomitant medication is ongoing, the start date will be imputed as the first day of the same month and year unless this partial start date is in same month as the first dose of study drug in which case the date of first dose of study drug will be used.
- If the stop date occurs before the start of study drug, the start date will be imputed as the first day of the month and year of the partial stop date.

If the start time is missing it will be imputed only in the case where the start date of the concomitant medication / event corresponds to the date of the first dose of study drug. The time will be imputed as the same time as the first dose of study drug. In all other cases the time will not be imputed.

### **6.6.2 Definition of First Study Day (SD1)**

First study day (SD1) is defined as the date of first administration of study treatment.

### **6.6.3 Definition of Baseline**

Baseline is defined as the last record or measure collected prior to the first dose of study medication.

If an assessment is collected on SD1 and either time of assessment or time of first dose is missing, then such assessment is considered as prior to the first dose. The exception to this rule are medications and AEs, which will be considered as concomitant or treatment-emergent, respectively.

### **6.6.4 Conversion factors**

The following conversion factors will be used to convert days into months or years, or vice versa, if needed:

1 week = 7 days,

1 month = 30.4375 days, and

1 year = 365.25 days.

The following conversion factors will be used for height and weight:

1 cm = 0.39370 in, and

1 kg = 2.20462 lb.

### **6.6.5 Missing Data**

All attempts will be made to minimize missing follow-up data. Data that are collected only at baseline will not be imputed.

Due to the early termination of the study no imputations for missing data will be applied with the exception of missing dates as described above. All summaries will be presented descriptively on available data.

## 7 DESCRIPTION OF STUDY POPULATION

### 7.1 Analysis Populations

The number of subjects meeting criteria for each analysis population will be tabulated.

### 7.2 Patient Disposition

The contribution of each centre to each of the two treatment arms and will be tabulated. The number of subjects attending each scheduled visit, discontinuing study medication prior to Day 28, terminating the study, reasons for early termination and time from randomization to study termination will be tabulated. The number of subjects considered screen failures and reason for screen failure will be tabulated. The number of subjects failing to meet any inclusion or exclusion criterion will be tabulated.

### 7.3 Baseline Characteristics

Baseline demographic data will be summarized.

#### 7.3.1 Medical History

Tabulations of previous and ongoing conditions at screening will be presented by randomized treatment group and overall. Medical history marked as Ongoing status as 'No' or with an end date prior to the date of randomization is considered previous. Medical history marked as Ongoing status as 'Yes' or an end date on or after the date of randomization are considered as concurrent disease. Conditions will be presented by MedDRA primary system organ class and preferred term.

#### 7.3.2 Concomitant medication

Prior medication refers to any medication that was stopped prior to the day of randomization. Concomitant medication refers to the new use or ongoing use of a medication at the randomization date up to and including the date of study termination.

Separate tabulations will be produced for prior or concomitant medications presented by randomized treatment group and overall for the Safety Analysis Set. Concomitant medications will be summarized using Anatomic Therapeutic Chemical (ATC) Level 2.

Additionally, the number and percentage of subjects taking any medication in the following categories will be tabulated. Cardiovascular and non-cardiovascular treatments will also be tabulated separately.

- beta-blocker
- ACE-inhibitor
- diuretic

- insulin or angiotensin receptor blocker (ARB)
- antibiotic or antiviral Rx
- corticosteroid

### **7.3.3 Physical Examination**

Physical examination results will be listed.

## 8 COMPLIANCE WITH STUDY MEDICATION AND DRUG ACCOUNTABILITY

For each visit the number of patients who were continued on any dose of study medication will be summarized.

In addition, drug accountability will be calculated for each visit.

Compliance at Visit x:

$$[(\text{Total amount of IP dispensed at visit x [initial weight of all bottles dispensed]} - \text{Total amount of IP returned for bottles dispensed at visit x [weight of all bottles returned]}) / \text{Total amount of IP dispensed at visit x}] * 100.$$

## 9 EVALUATION OF EFFICACY AND SAFETY

### 9.1 Primary Analysis for Efficacy

The primary efficacy outcome is the percent of patients who experience one of the following events during the first 28 days:

- All-cause mortality
- Requirement for ICU admission and/or ventilatory support
- CV complications\*:
  - HF or
  - AMI or
  - Myocarditis or
  - new sustained or symptomatic arrhythmia or
  - stroke

\*Outcome definitions can be found in Appendix 17.8 of the study protocol.

#### 9.1.1 Proportions of Subjects with an Event

All subjects who have met any condition of the composite outcome will be listed.

Due to the early termination of the study no analysis will be performed.

### 9.2 Secondary Efficacy Analyses

Due to the early termination of the study the Win Ratio of the Ordinal Outcome scale will not be generated. Ordinal outcome scale scores will be listed and summarized for each visit.

The change from baseline in each biomarker (hs-troponin, NT-proBNP, D-dimer) and inflammatory marker (hs-CRP, ferritin, IL-1 beta, IL-6, IL-10) over time will be summarized at each time point and graphically displayed. After review of the profiles over time, the following parameters may be calculated.

Emax 7	Maximum post-baseline change* (baseline-corrected change) up to the time of the Day 7 assessment; reported to 2 decimal places.
Emax 28	Maximum post-baseline change* (baseline-corrected change) up to the time of the Day 28 assessment; reported to 2 decimal places.
AUEC0-7	Area under the change from baseline curve from time zero to the Day 7

AUEC0-28	assessment; calculated using the linear trapezoidal rule; reported to 3 significant figures.
	Area under the change from baseline curve from time zero to the Day 28 assessment; calculated using the linear trapezoidal rule; reported to 3 significant figures.

\*maximum post-baseline change will be positive for biomarkers that increase relative to baseline over the time interval; or negative for those that decrease relative to baseline.

Assumptions for AUEC calculation:

- Time points other than pre-dose will use actual time point instead of nominal time points. If actual assessment time is missing the nominal time will be used.
- Values missing at time points after baseline and prior to last time point in the interval will not be imputed.
- If data at last time point is missing, AUEC will be calculated up to latest non-missing time point.
- AUEC calculation will not include unscheduled and repeat measurements.

Comparison of each parameter between the two treatment groups using an ANCOVA with fixed factors for treatment and the baseline value as covariate will be performed.

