4.1.4 Secondary Efficacy Parameters

The secondary efficacy parameters include the following:

- ...Win Ratio of Ordinal Outcome Scale endpoint:
 - 1) not hospitalized and no limitations of activities;
 - 2) not hospitalized, with limitation of activities, home oxygen requirement, or both;
 - 3) hospitalized, not requiring supplemental oxygen and no longer requiring ongoing medical care
 - 4) hospitalized, not requiring supplemental oxygen but requiring ongoing medical care
 - 5) hospitalized, requiring any supplemental oxygen;
 - 6) hospitalized, requiring noninvasive ventilation or use of high-flow oxygen devices;
 - 7) hospitalized, receiving invasive mechanical ventilation or extracorporeal membrane oxygenation (ECMO);
 - 8) MI or stroke diagnosed since randomization
 - 9) death.
- Change in hs-troponin from baseline to peak elevation during the 28-day treatment period
- Change in TNF-alpha from baseline to peak elevation during the 28-day treatment period

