9.2.12.2 Additional laboratory tests

In addition to local laboratory tests, frozen samples will be retained for the following tests to be analyzed by a central laboratory: hs-troponin, NT-proBNP, D-dimer, hs-CRP, ferritin, TNF-alpha, IL-1 beta, IL-6, IL-10, as well as CBD levels and additional parameters of interest. **These will not be used for genetic testing.**

Please see Appendix 17.2.2 for the exact schedule of all laboratory tests.

All samples will be stored at -70°C at the sites and will be shipped to the Central Laboratory in batches.

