#### 4.1.4 Secondary Efficacy Parameters

Secondary efficacy parameters include:

-Win Ratio of Ordinal Outcome Scale endpoint:

- 1) not hospitalized and no limitations of activities
- 2) not hospitalized, with limitation of activities, home oxygen requirement, or both;

- 3) hospitalized, not requiring supplemental oxygen and no longer requiring ongoing medical care
- 4) hospitalized, not requiring supplemental oxygen but requiring ongoing medical care
- 5) hospitalized, requiring any supplemental oxygen;
- 6) hospitalized, requiring noninvasive ventilation or use of high-flow oxygen devices;
- 7) hospitalized, receiving invasive mechanical ventilation or extracorporeal membrane oxygenation (ECMO);
- 8) MI or stroke diagnosed since randomization
- 9) death.

- Change in high sensitivity-troponin (hs-troponin) from baseline to peak elevation during the 28-day treatment period
- Change in Tumor Necrosis Factor (TNF)-alpha from baseline to peak elevation during the 28-day treatment period

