#### 4.1.5 Other Efficacy Parameters

Other efficacy parameters include:

- Percentage of patients developing any one of the primary endpoint components within 60 days post randomization
- CV mortality at 28 days post randomization
- Percentage of patients requiring dialysis within 28 days post randomization
- Win ratio of the Ordinal Outcome Scale endpoint within 60 days of randomization
- Patient Impression of Change Questionnaire (PICQ) at Day 28 and at Day 60
- Development of severe lymphopenia, defined as < 1000 cells/ microliter within 28 days post randomization
- Change in (elevation of) hs-troponin, NT-proBNP, D-dimer and in inflammatory markers (hs-CRP, ferritin, TNF-alpha, IL-1 beta, IL-6, IL-10) from baseline to Day 7 (AUC)
- Change from baseline to peak elevation of NT-proBNP, D-dimer and in inflammatory markers (hs-CRP, ferritin, IL-1 beta, IL-6, IL-10) during the 28-day treatment period
- Change from baseline to peak elevation of LDH during the 28-day treatment period
- Difference in cardiac magnetic resonance imaging (CMR) parameters: LVEF, LVEDV, LVESV, LAESV, ECV, GLS, LV mass, LGE extent and edema between the

---

two treatment groups after 4 weeks of study treatment (in a subset of patients at selected sites).

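### SAP 9.2 leaves out TNF-alpha, one of the three secondary endpoints, without analysing it or saying it was dropped

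*SAP*

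**What the plan says.** Protocol 4.1.4 and SAP 4.1.4 list the same three secondary efficacy parameters: the win ratio on the Ordinal Outcome Scale, the change in hs-troponin to peak, and, in the SAP's words, "Change in Tumor Necrosis Factor (TNF)-alpha from baseline to peak elevation during the 28-day treatment period". Protocol 11.2.2 handles the two markers together ("hs-troponin and TNF-alpha from baseline to peak elevation during the 28-day treatment period between the two treatment groups will be analyzed using an ANCOVA"), adjusting for each patient's starting level. SAP 4.1.5 also includes TNF-alpha in the Day 7 AUC parameter.

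Protocol 9.2.12.2 lists the central-laboratory assays as "hs-troponin, NT-proBNP, D-dimer, hs-CRP, ferritin, TNF-alpha, IL-1 beta, IL-6, IL-10, as well as CBD levels" and further parameters of interest. Protocol 9.1 schedules the marker samples at baseline and on Days 3, 5, 7 and 28.

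SAP 9.2 is where the marker data are analysed. It covers hs-troponin, NT-proBNP and D-dimer as biomarkers, and each "inflammatory marker (hs-CRP, ferritin, IL-1 beta, IL-6, IL-10) over time will be summarized at each time point and graphically displayed". Once the profiles have been reviewed, Emax and AUEC parameters may be derived for these markers and compared by ANCOVA. The same section removes the first secondary endpoint by name: "Due to the early termination of the study the Win Ratio of the Ordinal Outcome scale will not be generated". SAP section 2 describes an abbreviated set of outputs following early termination and says that changes from the protocol are noted.

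**The concern.** SAP section 4 retains TNF-alpha as a secondary endpoint, but the analysis section lists the markers without it. An endpoint that is retained should be analysed, and one that is cut should be recorded as cut. Here neither is done.

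The SAP is otherwise explicit about its larger cuts. It names the per-protocol set (5.3), sample size re-estimation (6.1), the interim analysis (6.3), multiplicity adjustment (6.4.1), subgroups (6.4.2), imputation (6.6.5), the primary comparison (9.1.1) and the win ratio (9.2). Against that background a reader cannot tell whether TNF-alpha was omitted deliberately, never assayed, or overlooked.

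The 9.2 list matters more than usual because SAP 6.2 and 6.4 make the marker data the only exception to the rule against statistical testing. The list decides what is summarised and plotted and what may be compared between arms. If assay data exist, seven markers that rank only as other parameters would be reported by visit and a secondary endpoint would not, with no reason on file. Adding or omitting TNF-alpha after unblinding would invite a question about selective reporting that a correction made beforehand avoids.

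**Working it through.** No sample size, power or alpha figure is involved. The check compares the marker lists and then searches the SAP for TNF-alpha.

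**Step 1: the lists side by side.**

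| Marker | Central laboratory (Protocol 9.2.12.2, 17.2.2) | Secondary, peak (SAP 4.1.4) | Other, Day 7 AUC (SAP 4.1.5) | Other, peak (SAP 4.1.5) | Analysed (SAP 9.2) |
|---|---|---|---|---|---|
| hs-troponin | yes | yes | yes | no | yes |
| NT-proBNP | yes | no | yes | yes | yes |
| D-dimer | yes | no | yes | yes | yes |
| hs-CRP | yes | no | yes | yes | yes |
| ferritin | yes | no | yes | yes | yes |
| IL-1 beta | yes | no | yes | yes | yes |
| IL-6 | yes | no | yes | yes | yes |
| IL-10 | yes | no | yes | yes | yes |
| **TNF-alpha** | **yes** | **yes** | **yes** | **no** | **no** |
| Count | 9 | 2 | 9 | 7 | 8 |

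Cannabidiol levels and samples stored for future testing are not counted as markers.

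**Step 2: the difference.** SAP 9.2 covers 3 biomarkers + 5 inflammatory markers = 8. The protocol schedules 9, and 9 − 8 = 1, which is TNF-alpha. SAP 9.2 contains no marker from outside the protocol list.

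**Step 3: is TNF-alpha handled elsewhere?** In the SAP text available for review it appears in the abbreviation list and in 4.1.4 and 4.1.5. It does not appear in sections 5 to 10. SAP 9.3.4 is confined to local laboratory data, and TNF-alpha is a central assay. Section 10 names no endpoint.

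**Step 4: status of the three secondary endpoints.**
- Win ratio: dropped by name; ordinal scores are still listed and summarised.
- hs-troponin: by-visit summary and plot assured; Emax/AUEC and ANCOVA optional.
- TNF-alpha: no summary, plot or optional parameter, and no statement that it was dropped.

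**Step 5: what is unplanned.** If the assay was run, the missing outputs are the change-from-baseline summaries at four scheduled visits (Days 3, 5, 7 and 28) and the plot. Emax and AUEC outputs are not counted, because they are not guaranteed for any marker. Emax 28 is also not stated to be the change to peak elevation, since its footnote allows negative values.

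**Step 6: a possible origin.** The SAP's lower-tier peak list reads "peak elevation of NT-proBNP, D-dimer and in inflammatory markers (hs-CRP, ferritin, IL-1 beta, IL-6, IL-10) during the 28-day treatment period", which is seven markers. It leaves out hs-troponin and TNF-alpha, the two placed in 4.1.4. The 9.2 list equals those seven plus hs-troponin: 7 + 1 = 8. This fits a list carried over with only one of the two secondary markers restored, but does not prove it.

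**The case against.** The strongest reply is that this is an abbreviated SAP for a trial that stopped early. Sections 2 and 10 announce limited-scope reporting, so anything not described may simply not be planned. Silence is not unique to TNF-alpha: dialysis, severe lymphopenia and the CMR parameters are also kept in SAP 4.1.5 with no matching analysis. SAP 6.2 promises tabulations of appropriate efficacy parameters and exempts marker data as a class from the no-testing rule, which might be read as covering TNF-alpha. The pages after SAP section 11 were not available for review and could mention it. The list comparison in Step 6 is also weaker than it looks: the protocol synopsis includes TNF-alpha in its lower-tier peak list, although Protocol 4.1.5 does not. Finally, nothing confirmatory is lost, because the primary comparison and multiplicity control have already been withdrawn.

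Much of this stands as a limit on size. The loss is descriptive output plus eligibility for an optional comparison. The origin of the omission is unproven, and unseen pages might alter the picture.

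It does not remove the inconsistency. The tabulation sentence in 6.2 covers only parameters deemed appropriate. The testing exception refers the reader to section 9, where the marker list is closed. The limited-scope wording names no endpoint, so it does not record this cut in the way section 2 promises. The other unmatched endpoints are lower-tier; TNF-alpha is secondary. If the unseen pages do cover it, 9.2 still needs to agree with them.

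**Conclusion.** The concern holds. SAP 4.1.4 and SAP 9.2 disagree about TNF-alpha: it is retained as a secondary endpoint, but is neither analysed nor declared dropped in the available text. The extent is 1 of 3 secondary endpoints and 1 of 9 central-laboratory markers. If the samples were assayed, summaries at four visits and one plot are unplanned.

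Confidence in the wording is high. The consequence depends on whether TNF-alpha data exist, which the documents do not show; if there are none, only an explanation is missing. Type I error, the primary endpoint and the safety conclusions are not affected. The SAP states that it will be approved before the blind is broken, so there is no suggestion that results drove the omission. It should be corrected before unblinding because it concerns a named secondary endpoint and costs almost nothing to settle.

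**What to change.** Before unblinding, do one of the following:

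- If TNF-alpha was assayed and is to be reported, add it to the inflammatory-marker list in SAP 9.2 so that it is treated like the other eight markers. The cost is one term in the text and one more run of the same program.
- If it was not assayed, or was cut deliberately, say so with the reason in SAP section 10. The cost is one sentence.

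As a separate point for the same edit, SAP section 10 rules out all inferential testing, whereas 6.2 and 6.4 make an exception for marker data and 9.2 provides for an ANCOVA. Section 10 should carry the same exception.
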